10.1.2 Primary Efficacy Analysis

A Bayesian logistic regression will be used to compare all-cause 6-hour mortality rate between the BE1116 and placebo arms, in the mITT Population.

Hypotheses:

Null Hypothesis (H_0): The all-cause 6-hour mortality rates in BE1116 is no better than control.

$$p_{kcentra} - p_{control} \geq 0$$

Alternative Hypothesis (H_1): The all-cause 6-hour mortality rate in BE1116 is lower than control.

$$p_{kcentra} - p_{control} < 0$$

Let y_i be the outcome of all-cause 6-hour death (1 = yes, 0 = no), the model is:

$$y_i \sim Bernoulli(p_i)$$

$$\text{logit}(p_i) = \beta_0 + \beta_1 \text{treatment}_i$$

where p_i is the probability of all-cause 6-hour mortality for subject i and $treatment_i$ is an indicator variable for treatment with BE1116. The coefficient β_0 is the effect of placebo on the primary outcome in the logit scale. The coefficient β_1 is the treatment effect of BE1116 over placebo on the primary outcome in the log-odds ratio scale.

While this model gives direct estimates of ORs, the absolute risk differences (primary outcome of interest) will be derived using posterior draws from the coefficients. We assume independent normal prior distributions for the regression coefficients of the form:

$$\beta_0 \sim Normal(\mu_0, \tau_0^2)$$

$$\beta_1 \sim Normal(\mu_1, \tau_1^2)$$

where, μ s and τ s are respectively the means and standard deviations of distributions.

The following priors are used:

$$\beta_0 \sim Normal(0, 10^2)$$

$$\beta_1 \sim Normal(0, 1^2)$$

These priors are centered at zero, which for β_1 corresponds to a priori no intervention effect. The prior for β_0 is noninformative, while the prior for β_1 is only very weakly informative and allows for considerable uncertainty; the 95% interval for β_1 on the OR scale ranges from 0.14 to 7.1.

The study will be considered a success and primary objective considered met if the posterior probability

$$\text{Prob}(p_{kcentra} - p_{control} < 0 | \text{data}),$$

of lower all-cause 6-hour mortality in the BE1116 arm compared with the placebo arm is greater than the success threshold.

For the final analysis the planned success threshold for the posterior probability will be 97.5%.

The Bayesian logistic regression model will be fitted via Markov Chain Monte Carlo (MCMC) methods in SAS (Version ≥ 9.4) using the PROC MCMC procedure. For each analysis, 4 MCMC chains will be run with a minimum burn-in of 3000 iterations and

sampling from a further 25,000 iterations for each chain. The Gelman-Rubin statistic \hat{R} will be calculated to evaluate whether the 4 chains have mixed sufficiently. The number of iterations per chain will be increased by 10,000 until the Gelman-Rubin statistic is below 1.01 for both β_0 and β_1 .

The posterior probability of:

$$p_{kcentra} - p_{control} < 0$$

will be calculated and compared to the efficacy threshold.

For this analysis, 95% credible intervals will be calculated and presented for $p_{kcentra}$, $p_{control}$ and their difference. Point estimates will be presented using the mean value of the posterior distribution.

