10.3.2 Efficacy Analyses

10.3.2.1 Primary Efficacy Endpoint Analyses

A Bayesian logistic regression will be used to compare all-cause mortality rate during the first 6 hours after randomization between the BE1116 and placebo arms, in the ITT Population.

Hypotheses:

Null Hypothesis (H_0): The all-cause 6-hour mortality rate in BE1116 is no better than control.

$$p_{kcentra} - p_{control} \geq 0$$

Alternative Hypothesis (H_1): The all-cause 6-hour mortality rate in BE1116 is lower than control.

$$p_{kcentra} - p_{control} < 0$$

Let y_i be the outcome of all-cause 6-hour death (1 = yes, 0 = no), the model is:

$$y_i \sim Bernoulli(p_i)$$

$$\text{logit}(p_i) = \beta_0 + \beta_1 \text{treatment}_i$$

where p_i is the probability of all-cause 6-hour mortality for subject i treatment intervention. The coefficient β_0 is the effect of placebo on the primary outcome in the logit scale. The

coefficient β_1 is the treatment effect of BE1116 over placebo on the primary outcome in the log OR scale. While this model gives direct estimates of ORs, the absolute risk differences (primary outcome of interest) will be derived using posterior draws from the coefficients. We assume independent normal prior distributions for the regression coefficients:

$$\beta_0 \sim \text{Normal}(\mu_0, \tau_0^2)$$

$$\beta_1 \sim \text{Normal}(\mu_1, \tau_1^2)$$

where, μ s and τ s are respectively the means and standard deviations of distributions.

For all interim and final analysis, the following noninformative priors are used:

$\beta_0 \sim \text{Normal}(0, 10^2)$, $\beta_1 \sim \text{Normal}(0, 1^2)$. These priors are centered at zero, which for β_1 corresponds to a priori no intervention effect. This noninformative prior allows considerable uncertainty; the 95% interval for β_1 on the OR scale ranges from 0.14 to 7.1 while avoiding unreasonable values.

The study will be considered a success and primary objective considered met if the posterior probability $\text{Prob}(p_{k\text{centra}} - p_{\text{control}} < 0 | \text{data})$ of lower all-cause 6-hour mortality in the BE1116 arm compared with the placebo arm is greater than the success threshold.

Interim analyses will occur when 1/4 (2000), 1/2 (4000), and 3/4 (6000) of the targeted 8000 subjects have data for the primary outcome. A group sequential approach will be utilized (see [Section 10.3.4](#)).

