This Statistical Analysis Plan (SAP) provides a detailed and complete description of the planned statistical analyses of the study BE1116_3006 [Evaluation of BE1116 (4-factor prothrombin complex concentrate [4F-PCC]) in patients with traumatic injury and confirmed or suspected acute major bleeding to improve survival] to support the Clinical Study Report (CSR).

This SAP complies with the International Council for Harmonisation (ICH) E9 ‘Statistical Principles for Clinical Trials’ and E9(R1) ‘Statistical Principles for Clinical Trials: Addendum on Estimands and Sensitivity Analysis in Clinical Trials’, and is based upon the following study documents:

- Clinical Study Protocol (CSP) Amendment 2 dated 06 February 2024
- Electronic Case Report Form (eCRF), Version V5.0, dated 04 April 2024

All decisions regarding the final analysis of the study results, as defined in this SAP, have been made before database lock (DBL) of the study data.

Deviations from the analyses in this SAP will be detailed in the CSR.

4 Study Design

This is a phase 3, prospective, multicenter, randomized, double-blind, placebo-controlled, parallel-group, large simple trial to investigate the efficacy and safety of a single intravenous (IV) infusion of BE1116 in subjects who have traumatic injury, with confirmed or suspected acute major bleeding and / or predicted to receive a large volume blood product transfusion.

Randomization will be in a 1:1 ratio (BE1116:placebo) using randomized block design with blocks within each site. The time of randomization is defined as the time at which the selected Investigational Product (IP) study kit is opened by the trauma team (or other applicable site staff) for IP reconstitution and administration.

The IP infusion will be given in addition to the study site’s standard resuscitation methods and protocol. All subjects will receive standard of care according to the study site’s normal clinical practice at all times during the study. Standard of care should not be interrupted or forgone to enable subject participation in the study.

The study consists of (i) a Screening and Randomization (Enrollment) Period, (ii) a Treatment Period, and (iii) an In-hospital Follow-up Period.

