4.4 Determination of the Sample Size

The originally planned sample size of 8000 subjects (4000 per treatment arm) was determined to achieve 80% power while controlling for a one-sided type I error of 0.025 testing for superiority, accounting for 3 interim analyses.

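### The MCMC extension rule does not control the Monte Carlo error of the posterior probability compared with 97.5%, so a result very close to the cut can pass or fail by random seed; numerical integration removes this at no cost

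*SAP*

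**What the plan says.** SAP 10.1.2 fits a logistic model with an intercept and one treatment indicator by PROC MCMC. Success is a hard cut: "For the final analysis the planned success threshold for the posterior probability will be 97.5"%. The run length is set by "4 MCMC chains will be run with a minimum burn-in of 3000 iterations and" then "sampling from a further 25,000 iterations for each chain", so at least 100,000 draws are retained. The only rule for adding draws is "The number of iterations per chain will be increased by 10,000 until the Gelman-Rubin statistic is below 1.01", applied to β0 and β1. The posterior probability of lower mortality on BE1116 then "will be calculated and compared to the efficacy threshold".

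SAP 10.4 applies the same 97.5% cut to the three gated secondary endpoints, which SAP 10.2.2 to 10.2.4 analyze in the same or a similar way.

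The readable text of SAP 10.1.2 gives no limit on the Monte Carlo error of this probability, no minimum effective sample size for it, and no rule for a result within simulation error of the cut. Seeds and the effective sample size of the success indicator appear only in the simulation report (SAP 16.2.1 and 16.2.6), which SAP 16.2 says no longer applies to the planned analysis.

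**The concern.** R-hat compares variation between chains with variation within chains for a coefficient. It can be satisfied while the estimated share of draws with β1 below zero still has an error in the third decimal place. Because success turns on whether that share exceeds 0.975, a result close enough to the cut could be declared a success with one seed and a failure with another. The same applies at each step of the gated sequence.

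The error is also avoidable. The model has no covariates, so the data reduce to four counts (deaths and subjects in each arm), and the probability can be computed without simulation.

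**Working it through.** **Inputs**
- From SAP 10.1.2: cut 0.975; 4 × 25,000 draws; R-hat below 1.01 for β0 and β1; priors N(0, 10²) and N(0, 1²).
- From the SAP simulation report (16.2.4 and 16.2.5): 10% placebo mortality; a 20% relative reduction gives 8%.
- Final sample size: not stated. SAP 4.5 says the review at 1000 subjects took place, and SAP 12 says the study stopped before the first interim analysis, planned at 2000. Assumed: 500 to 900 per arm.
- Sampler and effective sample size (ESS): not stated beyond PROC MCMC. Assumed ESS: 5,000 to 100,000.

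**1. The plan's own figures.** The prior for β1 gives exp(±1.96) = 0.14 to 7.10, matching the protocol: "the 95% interval for β_1 on the OR scale ranges from 0.14 to 7.1". Re-simulating the original group sequential design gave 82.9% overall success at 10% v 8%, as in SAP Table 4. The null case gave 2.2% against the stated 1.94%; nothing below uses it. The plan states no Monte Carlo error for the final analysis, so there is none to reproduce.

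**2. Monte Carlo standard error at the cut.** SE = √(0.975 × 0.025 / ESS) = √(0.024375 / ESS).

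| ESS | SE | ±1.96 SE (percentage points) |
|---|---|---|
| 100,000 (independent draws) | 0.0005 | 0.10 |
| 20,000 | 0.0011 | 0.22 |
| 15,000 | 0.0013 | 0.25 |
| 5,000 | 0.0022 | 0.43 |

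**3. Does the R-hat rule add draws?** A tuned random-walk Metropolis sampler, standing in for PROC MCMC, was run with 4 chains, 3,000 burn-in and 25,000 draws each, for 200 seeds per data set at 650 per arm. R-hat stayed below 1.001 in every run, so no extension was triggered. The ESS of the success indicator was about 16,000 to 20,000.

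**4. Fixed data, different seeds.** The event p_kcentra < p_control is the event β1 < 0. With e deaths among n subjects per arm (0 = placebo, 1 = BE1116), its exact probability is the integral over β1 < 0 of a density proportional to exp{e0·β0 − n0·log(1+exp β0) + e1·(β0+β1) − n1·log(1+exp(β0+β1)) − β0²/200 − β1²/2}.

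| Deaths, placebo v BE1116 (650 per arm) | Quadrature | Seeds above 0.975 |
|---|---|---|
| 80 v 58 | 0.97499 | 54% |
| 59 v 40 | 0.97495 | 50.5% |
| 58 v 39 | 0.97599 | 78.5% |
| 69 v 48 | 0.9778 | 100% |

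At 600 per arm, 90 v 67 deaths gives 0.97438, a fail. The random-walk runs had SD about 0.0012 and passed in about 30% to 38% of cases. An independence sampler with ESS near 100,000 (SE 0.0005) passed in about 9%.

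**5. Width of the problem in deaths.** In that example, one fewer BE1116 death gives 0.9793 and one more gives 0.9685. The distances from 0.975 are 0.0043 and 0.0065, about 4 and 6 times an SE of 0.0011.

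**6. Chance of being affected.** On the normal-deviate scale an SE of 0.00109 becomes 0.00109 / 0.0584 = 0.0187, where 0.0584 is the normal density at 1.96. The density of the observed deviate at the cut is at most 0.399, so the chance of disagreeing with the exact posterior is at most 0.399 × 2 × 0.399 × 0.0187 = 0.006. The same formula gives 0.003 for an SE of 0.0005 and 0.012 for 0.0022.

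At 600 per arm and SE 0.00109, disagreement is 0.08% at 10% v 10% and 0.44% at 10% v 8%. Type I error is 2.24% and power at 10% v 8% is 21.1%, with or without Monte Carlo noise. At 500 to 900 per arm and ESS 15,000, two seeds disagree in about 0.14% of trials under the null, 0.7% to 0.9% at 10% v 8%, and about 1.0% at 10% v 7%.

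**The case against.** Four chains, at least 100,000 draws and R-hat below 1.01 is an explicit and reasonable specification for a two-parameter model, and nothing in it is contradictory. The SAP never names a Metropolis sampler, so the ESS is the reviewer's assumption and a more efficient sampler narrows the band. The sponsor's simulation programs already set seeds, recorded the ESS of the success indicator and ran further diagnostics on it (SAP 16.2.1, 16.2.6, 16.2.7). All of this stands, and it limits the size of the point. The simulation report is not a rule for the final analysis, however, and the rule that does apply leaves the decision quantity uncontrolled.

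A reader might infer three stronger things.
- **The trial's result depends on the seed.** Only isolated combinations of counts are affected, and one death either way usually removes the dependence.
- **Type I error is inflated.** Errors in the two directions nearly cancel, and the calculation shows no inflation.
- **The plan has no seed.** This cannot be concluded. The SAP contents list Bayesian SAS code as section 16.1.1, but the code is not in the readable text and may fix a seed. A fixed seed makes a run reproducible, but a result near the cut would still depend on which seed was chosen.

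**Conclusion.** The point holds in a limited form. The stated rule does not control the Monte Carlo error of the probability that decides success, and a result within about 0.1 to 0.4 percentage points of 97.5% can pass or fail by seed. For a tuned random-walk sampler the chance of contradicting the exact posterior is at most about 0.6% per test. Over the assumed ESS range that bound runs from about 0.3% to 1.2%. Operating characteristics are essentially unchanged.

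The SE at a given ESS is arithmetic. The ESS itself, the arm sizes and the mortality rates used for the probabilities are assumptions. This is a refinement worth making because it is free. It is not an error that undermines the primary analysis.

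**What to change.** State in SAP 10.1.2 and 10.4 that the posterior probability compared with 97.5%, for the primary and each gated secondary endpoint, is obtained by numerical quadrature of the specified two-parameter posterior. Keep PROC MCMC for point estimates and credible intervals. Model, priors, threshold and populations do not change. The cost is one SAP sentence and a few lines of code before database lock, with trivial run time.

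If MCMC is kept for the decision, state the seed, report the Monte Carlo SE of the probability, and extend sampling until that SE is small relative to the distance from 97.5%. A fixed limit is less satisfactory: an SE of 0.0002 needs an ESS of 0.024375 / 0.0002² ≈ 609,000 and still leaves a narrow band. The distance-based rule can also become impractical. For 80 v 58 deaths at 650 per arm the distance is 0.00001, and an SE merely equal to it needs 0.024375 / 0.00001² ≈ 240 million effective draws. Quadrature avoids both problems.

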10.1.3 Supplemental Analysis for the Primary Endpoint

Primary analysis will also be conducted in the ITT and PP populations. The only element of the estimand that changes is the population of interest, which is subjects with traumatic injury (ITT population) and subjects with traumatic injury and no protocol deviation that would potentially affect the assessment of the primary endpoints (Per-protocol population).

The results will be presented in a separate table. Missing data handling is described in [Section 8.1](#)

10.1.4 Subgroup Analyses of Primary Endpoint

Subgroup analyses will be used to help determine whether the treatment effect for the primary endpoint is homogeneous across the study population.

Subgroups of interest for this study are as follows:

- Mechanism of trauma injury: penetrating, or blunt .
- Presence of Head Injury: as indicated by Abbreviated Injury Scale(AIS) score > 0 in the “head” region).
- Sex: male, or female.
- Race: White, Black or African American, or Other.
- Age (< 18 years, 18 to 25 years, 26 to 64 years, or > 64 years).

- Weight-based dosing (2000 IU, or 3000 IU).
- IP administration start of infusion (Up to 45 minutes after hospital arrival, or > 45 minute to 90 minutes after hospital arrival.)
- Mode of transport: helicopter, ambulance, or self-presenting.
- RABT: $RABT \leq 2$, or $RABT > 2$.
- Blood pressure at admission: < 70 Systolic, or ≥ 70 Systolic mmHg.
- Glasgow Coma Scale at admission: by categories ≤ 8 , 9 to 12, 13-14.
- Injury Severity Score using the following categories:
 - Mild (1-8)
 - Moderate (9-15)
 - Severe (16-24)
 - Profound (≥ 25)
- Whether Fibrinogen was administered before study treatment: yes/no.
- Whether Cryoprecipitate was administered before study treatment: yes/no.
- Whether Tranexamic Acid was administered before study treatment: yes/no.

For the subgroup analysis the primary analysis model will be calculated within each level of the subgroup variable. For mechanism of trauma injury, a subject can have both blunt and penetrating injuries. In this case, the subject is included in both subgroups.

Credible intervals for the mortality within each treatment arm and the posterior probability for a lower mortality in the active treatment arm will be presented for each level of the subgroup variables.

Subgroup analysis of penetrating versus blunt trauma injury will provide evidence of BE1116 efficacy and safety in these populations with different mechanisms of traumatic injury. Blunt trauma, also called nonpenetrating trauma or blunt force trauma, is an injury to the body caused by forceful impact, injury, or physical attack with a dull object or surface. It is in contrast to penetrating trauma, in which an object pierces the body surface, causing an open wound ([NIGMC, 2018](#)).

Well documented subpopulation analysis of sex differences has shown that males experience an increased risk of mortality and hospital length of stay, and a higher incidence of complications, when compared with females ([Liu T, 2015](#)).

Subjects of unknown sex will be excluded from this subgroup analysis. If the proportion of subjects with unknown is unexpectedly high ($> 1\%$) a sensitivity analysis may be conducted, where the analysis will be repeated first by setting the sex to 'male' for all subjects with unknown gender and then again by setting it to 'female' instead.

Subgroup analysis of subjects aged < 18 years is important to confirm there are no important differences between teenagers and young adults ([Liras IN, 2016](#)).

Subjects weighing between 50 and 75 kg will receive 2000 IU and subjects weighing > 75 kg will receive 3000 IU. This dosing regimen was designed to ensure equivalent doses of IP per kg body weight, so that all subjects receive equivalent blood concentrations of the coagulation factors present in the IP. This is the standard dosing used for non-trauma subjects. However, it is possible that the total dose of IP, rather than the blood concentration of IP, will be most important in trauma patients with acute hemorrhage who are at risk of the lethal triad. This analysis will aim to determine whether total dose impacts outcomes. Subjects' planned dosing group will be used regardless of the actual weight or partial dose received.

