4.2 Study Treatments

The active study treatment is BE1116 (4F-PCC) containing human coagulation Factors II, VII, IX, and X, Protein C, and Protein S, powder for reconstitution with sterile water for injection.

A single dose will be administered by IV infusion. The dose is dependent on body weight (estimated or measured):

- Weight < 75 kg (< 165 lbs): 2000 IU
- Weight \geq 75 kg (\geq 165 lbs): 3000 IU

Patients will receive either BE1116 or placebo.

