6.1.4 Safety Population

The Safety Population will include all subjects in the ITT Population who receive a complete or partial dose of BE1116 or placebo, based on the treatment actually received.

7 General Considerations

Datasets will be created according to Clinical Data Interchange Standards Consortium (CDISC) standards. Study data will be provided in Study Data Tabulation Model (SDTM) format. Analysis data will be provided in Analysis Data Model (ADaM) format.

SAS version 9.4 or higher will be used to perform all data analyses.

Summaries of continuous variables will be in terms of the number of observations, mean, standard deviation, median, first quartile (Q1), third quartile (Q3), minimum and maximum.

Categorical variables will be summarized using frequency counts and percentages.

Analyses that use other descriptive statistics will have the specific descriptive statistics identified with the analysis in the applicable SAP section.

For all Bayesian analysis, posterior credible intervals will be reported, based on the quantiles of Markov Chain Monte Carlo (MCMC) samples. Point estimates will be based on posterior means.

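### SAP 10.1.4 asks whether the treatment effect is homogeneous but lists no between-level contrast, and its overlapping mechanism levels are not recorded as a change in SAP section 5

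*SAP*

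**What the plan says.** The aim in SAP 10.1.4 is: "Subgroup analyses will be used to help determine whether the treatment effect for the primary endpoint is homogeneous across the study population". Two more specific questions follow. For 2000 IU against 3000 IU: "This analysis will aim to determine whether total dose impacts outcomes". For subjects under 18, the analysis "is important to confirm there are no important differences between teenagers and young adults".

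The method is: "For the subgroup analysis the primary analysis model will be calculated within each level of the subgroup variable". The listed output for each level is: "Credible intervals for the mortality within each treatment arm and the posterior probability for a lower mortality in the active treatment arm will be presented". SAP 10.2.6 applies the same approach to the secondary efficacy endpoints.

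Protocol 10.3.2.3 had planned models with covariate-by-treatment interaction terms, covering mechanism, sex, age and dose group among others. The SAP revision history and SAP 5.1 state that these sensitivity analyses were removed because of early termination and the reduced sample size, and that groupings were moved to the subgroup analysis.

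For mechanism of injury, protocol 10.3.2.2 sets any penetrating injury against blunt injury. SAP 10.1.4 uses penetrating and blunt as two levels and says of a subject with both: "In this case, the subject is included in both subgroups". Neither SAP 5.1 nor 5.2 nor the revision history lists this redefinition.

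**The concern.** Homogeneity is a question about the difference between effects in different levels. The listed outputs describe each level on its own. The posterior probability of lower mortality moves towards 1 as a level grows, even when the effect stays the same, so unequal probabilities do not imply unequal effects. A reader could form a between-level comparison only informally, from four arm-level intervals for each pair of levels. The interaction models that would have supplied it were removed and nothing took their place.

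The mechanism levels add a second difficulty. They share subjects, so their posteriors are dependent and cannot be contrasted as if they came from separate groups. A true penetrating-blunt difference can also be diluted. A reader who compares the protocol with SAP section 5 would not learn that the grouping changed.

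What is at stake is the reading of supportive tables: 15 variables on four endpoints.

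**Working it through.** **Plan figures reproduced.** The prior for the treatment coefficient is Normal(0, 1) on the log odds ratio. exp(±1.96) = 0.14 to 7.1, as SAP 10.1.2 states. A simulation of the original design with a normal approximation to this posterior gave 83.0% success at 10% versus 8% (SAP Table 4: 82.9%) and 1.99% under the null (stated 1.94%). The approximation is therefore adequate here.

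**Inputs.** Placebo 10% comes from SAP 16.2; 8% is the 20% relative reduction in Table 4. Final N is not given. SAP 4.5 says the 1000-subject safety review took place, and SAP section 12 says the study stopped before the 2000-subject interim. I assume an mITT N of 800 to 2000. The upper end is a ceiling, because the mITT also drops subjects who were undosed, had a Glasgow score of 15 or were not transfused before randomization. I also assume an 80/20 split and the same true effect in both levels.

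**Dependence on level size.** With n per arm in a level:
- log OR: d = ln(0.08/0.92) − ln(0.10/0.90) = −0.245
- variance: v = 1/(0.09n) + 1/(0.0736n)
- posterior mean d/(1+v) and variance v/(1+v), so Pr(lower mortality) ≈ Φ(0.245/√(v(1+v)))

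| N | Level | n per arm | v | Pr at expected counts | Simulated median |
|---|---|---|---|---|---|
| 800 | large | 320 | 0.0772 | 0.80 | 0.80 |
| 800 | small | 80 | 0.3087 | 0.65 | 0.67 |
| 2000 | large | 800 | 0.0309 | 0.92 | 0.92 |
| 2000 | small | 200 | 0.1235 | 0.74 | 0.75 |

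Grid integration of the SAP model gives medians of 0.81 and 0.68, then 0.92 and 0.75. The small gap at 80 per arm reflects whole-number death counts.

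Chance variation adds to this. In two equal levels with the same effect, the two probabilities differ by more than 0.30 in 41% of simulated trials at 200 per arm per level and in 31% at 500.

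**What a contrast would look like.** For two equal levels the contrast in log OR has variance 2v/(1+v).
- n = 200: √(2 × 0.1235/1.1235) = 0.469; exp(1.96 × 0.469) = 2.5 (simulated 2.6)
- n = 500: √(2 × 0.0494/1.0494) = 0.307; exp(1.96 × 0.307) = 1.8 (simulated 1.8)

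On the risk-difference scale, ignoring the prior, the half-width is 1.96 × √(2 × (0.09 + 0.0736)/n), which is 7.9 points at n = 200 and 5.0 points at n = 500.

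**Volume.** The levels are 2+2+2+3+4+2+2+3+2+2+3+4+2+2+2 = 37 over 15 variables, so 37 − 15 = 22 contrasts per endpoint. When the odds ratio is the same in both levels, a 95% interval for the ratio of odds ratios excludes 1 in 2.8% to 4.5% of simulated trials. The expected number of false signals per endpoint is then 22 × 0.028 = 0.6 to 22 × 0.045 = 1.0.

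**Scale.** One common odds ratio of 0.78 gives a risk difference of −1.1 points at a placebo rate of 5% (odds 0.0526 × 0.78 = 0.0411, rate 3.9%). At 25% it gives −4.4 points (0.3333 × 0.78 = 0.26, rate 20.6%). Homogeneity on one scale is not homogeneity on the other.

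**Mechanism overlap.** The documents give no share of subjects with both injuries. If mixed subjects respond like blunt ones, the penetrating level is diluted instead of the blunt one under the SAP grouping, and the blunt estimate is undisturbed. If they respond like penetrating ones, the contrast shrinks by m/(b+m), where m is the mixed share and b the blunt-only share. For assumed m of 5% to 20% and 50% to 70% of the rest blunt, this is 0.05/(0.665+0.05) = 7% to 0.20/(0.40+0.20) = 33%.

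**The case against.** The removal was deliberate, disclosed and reasoned. The sample shrank, and the contrasts are too imprecise to establish homogeneity: in simulation, a 40% versus 0% relative reduction would be flagged in only 16% of trials (200 per arm per level) to 39% (500). Protocol 10.3.2.2 states the same aim, also without a contrast, and the SAP promises only to help determine homogeneity. All of this stands, and it is why the request is for an exploratory estimate, not a test. A wide contrast interval shows how little is known; separate probabilities hide it.

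Much of the within-level reporting may already be covered. SAP section 7 says: "For all Bayesian analysis, posterior credible intervals will be reported". SAP 10.1.2 reports the interval for the arm difference, and the subgroup fits reuse that model. This also stands, so on that item only confirmation is needed. It does not supply a comparison between levels.

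Four stronger readings are tempting and are not supported:
- That subgroups will be declared positive at 97.5%. The SAP sets no per-level rule; that threshold belongs to the primary and gated secondary tests.
- That the interaction models were dropped silently. The revision history and 5.1 report it.
- That the overlap is hidden. SAP 10.1.4 states it plainly; only the section 5 entry is missing. The protocol also does not say in so many words that its blunt level excludes mixed injuries. That is the natural reading of its wording.
- That homogeneity should be judged on odds ratios alone. The estimand is a difference in proportions, so the risk-difference scale has to be shown.

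**Conclusion.** The point holds as a reporting gap worth closing. SAP 10.1.4 sets a homogeneity question and two between-level questions, and its listed output answers none of them directly. Under an identical effect (assumed 10% versus 8%, 80/20 split, N = 800 to 2000), the median posterior probability differs between large and small levels by about 0.13 to 0.17 through size alone. The exact figures rest on those assumptions; the direction follows from the formula.

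The mechanism item is narrower. It is an unlisted change of grouping, with a dilution that cannot be fixed from the documents. A reader might infer that the efficacy conclusion is at risk. It is not: the primary analysis, its threshold and the gated secondary sequence do not use these tables.

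**What to change.** In SAP 10.1.4, carried to the secondary endpoints through 10.2.6:

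1. Confirm that each level reports subjects and deaths per arm, and the posterior mean and 95% credible interval of the risk difference, as in 10.1.2.
2. For each variable with disjoint levels, report the posterior mean and 95% credible interval of the difference in treatment effect between each level and a named reference level. Give it on the risk-difference scale and also as a ratio of odds ratios, from the per-level draws already planned. State the implied prior on the latter: exp(±1.96√2) = 0.06 to 16.
3. Base any statement on homogeneity on these contrasts, and label them exploratory and unadjusted for multiplicity. Note that the 2000 versus 3000 IU contrast is confounded with body weight, because SAP 4.2 sets dose by weight, so it cannot isolate a dose effect.
4. Use disjoint mechanism levels (any penetrating versus blunt without penetrating), or add a disjoint table beside the overlapping one. In either case list the redefinition in section 5.

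The cost is SAP wording and extra summaries, with no new data. The downside is wide intervals: the ratio of odds ratios spans a factor of roughly 1.8 to 2.6 each way for two equal levels of 500 down to 200 per arm. Most contrasts will show only that homogeneity is not established, and some false signals should be expected among 22 per endpoint.
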